4.5. Randomisation Procedure

All subjects that meet the inclusion and exclusion criteria will be randomised to one of two treatment arms. Each arm examines the non-CE marked investigational product and one of the CE marked comparator investigational products in the following order:

- Arm A: The non-CE marked investigational product, then one of the five CE marked comparators investigational products.
- Arm B: One of the five CE marked comparators investigational products, then the non-CE marked investigational product.

There will be one randomisation list for the subjects normally using a 1-piece product and one for subjects normally using a 2-piece product. This is to stratify the two types of subjects to the treatment arms. The randomisations list will consist of blocks of ten, and centralised.

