11.1. Statistical design, method and analytical procedures

The primary objective will be evaluated by analysing the primary and secondary endpoints. These analyses are carried out by Medical Affairs, Coloplast A/S and are described in the following. The secondary objective regarding the [REDACTED] will be evaluated out by [REDACTED] and [REDACTED]

All baseline measurements, endpoints and other measurements (see Appendix 1 - Endpoints) will be summarized by descriptive statistics and/or listed. Endpoints and other measurements will be summarized by product, product type (1- or 2-pc) and visit, if relevant. Descriptive statistics for continuous variables are presented with N, Mean, SD (standard deviation), Median, Min and Max), where N denotes the number of subjects contributing with non-missing data. For discrete variables, descriptive statistics are presented with N and percentage, where percentage is based on the total number of subjects/observations with non-missing data.

As it is an exploratory study no adjustment for multiple testing will be applied.

All statistical analyses are made with SAS version 9.4 (SAS Institute Inc., Cary, NC)

Definition of analysis populations

Intention to Treat (ITT), Safety and Per Protocol (PP) populations will be defined at a formal data review meeting just before database lock. As a minimum, the data manager, the clinical manager and the statistician will be involved in the classification of subjects.

The ITT population (full analysis set) will be constituted by all randomised subjects with valid informed consent who have been exposed to at least one product, and with valid information on at least one product with respect to either primary or secondary endpoints.

The PP population will be constituted by a subset of ITT subjects who fulfilled the inclusion/exclusion criteria and did not violate the protocol in a serious way

Any exclusion of subjects from the PP/ITT population must be documented. Invalid individual data points may be omitted from analysis even though the corresponding subject is part of the ITT or PP population. Any exclusion of data points will be documented.

The Safety population will constitute by subjects who have given informed consent.

All statistical analysis will be based upon the ITT and PP population whereas adverse events and Device deficiencies will be assessed based on the safety population.

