The total DET score from Visit 2 and 3 will be analysed by a linear mixed model similar to the model for the primary endpoint, except that the random interaction effect of product and subject is not included, as there is only one measurement per subject for each product. The endpoints regarding individual item scores (discoloration, erosion and tissue overgrowth) can be analysed by the same model, if relevant.

The discoloration area and intensity at steady state will be analysed by the same model as described for the primary endpoint. For these analyses the data from the individual skin photos are the observational unit.

The endpoints regarding frequency in the past 14 days by end of treatment (of itching, pain and burning) will be analysed similar to the analysis of total DET score. Instead of a mixed model, a generalized linear mixed model, namely a proportional odds model, will be applied for the analysis as the response is on a 5-point scale. Proc Glimmix will be applied for the analysis.

Analyses of exploratory endpoints

The leakage area and leakage diameter at steady state will be analyzed by the same model as the discoloration area and intensity described under secondary endpoints.

The median wear time will be analyzed by the same model as the total DET score. The median wear time per subject is based on data from the 3 last weeks in each period.

The three scores from the leakage scale questionnaire (emotional impact, usual/social activities, coping/control) as well as the total score and the sub-scores (discreteness, comfort, confidence and social life) from the quality of life questionnaire will be analyzed by the same model as the total DET score.

The endpoint regarding feeling of security as well as the 3 endpoints regarding handling will be analyzed by the same proportional odds model as described for the frequency of itching in the past 14 days by end of treatment.

The proportion of subjects preferring test product will be compared with the proportion preferring the comparator by a test in the binomial distribution, testing the hypothesis that the proportions are equal.

Analyses of safety endpoints

Adverse events will be listed and summarized, if relevant.

CONFIDENTIAL

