11.3. Level of significance and power

A significance level of 5% will be applied. For a description of the power see section 11.2 above.

CONFIDENTIAL

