		Is there discoloration of peristomal skin with complications? (Yes/No) by end of treatment	Is there discoloration of peristomal skin with complications? (pain, shiny, indurated, hot, itching, burning)? (Yes/no)	Skin condition (DET score)	Investigator (subject)	X	X	X			
		Is there damage to the lower layers of the skin with complications? (moisture, bleeding or ulceration)? (Yes/no)	Is there damage to the lower layers of the skin with complications (moisture, bleeding or ulceration)? (Yes/no)	Skin condition (DET score)	Investigator	X	X	X			
		Is there raised tissue above skin level with complications? (bleeding, pain or moisture)? (Yes/no)	Is there raised tissue above skin level with complications (bleeding, pain or moisture)? (Yes/no)	Skin condition (DET score)	Investigator (Subject)	X	X	X			
		Stoma behaviour	Did your stoma behave differently from normal since your last visit/call? (Yes/No)	Visit CRF	Subject	X	X	X			
			-If yes, please specify	Visit CRF	Subject	X	X	X			
			How was the feeling of security while wearing the product? (5-point scale from Very poor to Very good)	Visit CRF	Subject	X	X	X			
				How did you find cutting the baseplate? (5-point scale from very difficult to very easy)	Visit CRF	Subject	X	X			
Handling		21. Feeling of security									
		22. Cutting the baseplate	(5-point scale by)	end of treatment	Visit CRF	Subject	X	X			

CONFIDENTIAL

CONFIDENTIAL

Type of endpoint	Group of endpoint	Description of Measurement	Derived from	Origin	Assessed by	V1	V2	V3	Calls	Product change
		change at steady state	Estimated by [REDACTED] from photos of the baseplate	Leakage (photos of baseplate)	Sponsor, from photos taken by subjects	X	X	X		
		29. Leakage area (cm ²) by baseplate								
		change at steady state								
		30. Total HQoL score (0-92) by end of treatment	Calculated based on the questions from the Quality of life questionnaire	Quality of life questionnaire (Ostomy-Q)	Subject fills in the questions and the sponsor calculates the score	X	X	X		
		31. Discreetness score (0-24) by end of treatment								
		32. Comfort score (0-24) by end of treatment								
		33. Confidence (0-24) score by end of treatment								
		34. Social life (0-20) score by end of treatment								
Preference		35. Proportion of preference of test product or SC?	Which product do you prefer? (The product from the first test period, the product from the second test period?)	Visit CRF	Subject	X				

CONFIDENTIAL

CONFIDENTIAL

[figure not shown]

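### The binomial preference test ignores the randomised order: with balanced arms it is valid but loses power, and with unbalanced respondents its estimate is also biased

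*Combined protocol and SAP*

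**What the plan says.** Section 11.1, on the exploratory endpoints, gives preference one sentence: the share favouring the test product is to be "compared with the proportion preferring the comparator by a test in the binomial distribution, testing the hypothesis that the proportions are equal". It names no sequence, period or product-type term and does not say whether the test is run overall or by product type.

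Appendix 1 (endpoint 35) records the answer by period, not by product: "Which product do you prefer? (The product from the first test period, the product from the second test period".

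Section 4.5 randomises the order. Arm A uses the test product first and Arm B the comparator first. The order is also stratified by product type: "There will be one randomisation list for the subjects normally using a 1-piece product and one for subjects normally using a 2-piece product". On blocking it says: "The randomisations list will consist of blocks of ten, and centralised". No allocation ratio is written, but section 11.2 counts 20 per arm within a product type and 40 per arm overall, which implies 1:1.

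The primary model in section 11.1 contains period, period-by-product, product type and product-by-type. The other modelled endpoints use that model or a close relative. Section 11.3 states: "A significance level of 5% will be applied". Sidedness is not given.

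**The concern.** In a two-period crossover, subjects may favour a product for its position, for example because it is the one they used most recently. The question can be answered only after both periods and is worded by period, so such a leaning would enter the data directly. A test that compares the pooled share preferring test with one half does not separate position from product.

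Two things are at stake. One is power: an order effect makes the pooled count less variable than the binomial test assumes. The other is bias: if more subjects answer in one arm than in the other, part of the order effect enters the estimated product preference. Section 4.3 lists the assessment of user preference among the advantages of the crossover design, so the result is likely to be read with interest.

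**Working it through.** The plan states no power or expected share for preference, so there is no figure of its own to reproduce.

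**Inputs from the document.** There are two orders, implied 1:1 (sections 4.5 and 11.2). Of 96 randomised subjects, 80 are planned as evaluable (11.2). The level is 5% (11.3), taken as two-sided.

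**Assumptions not in the document.** Let q be the share choosing the later product when the products are equal, with a range of 0.50 to 0.75. The product effect is 0.65 on the logit scale. The respondent splits by arm are 40/40, 44/36, 36/44 and 48/32 (A/B).

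**Step 1. Expected pooled share with equal products.** Test comes first in Arm A and second in Arm B, so

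E = [nA(1 − q) + nB·q] / (nA + nB).

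- 40/40, any q: 40(1 − q + q)/80 = 0.500. The order effect cancels.
- 44/36, q = 0.65: (44 × 0.35 + 36 × 0.65)/80 = (15.4 + 23.4)/80 = 0.485, a bias of −1.5 points.
- 36/44, q = 0.65: (12.6 + 28.6)/80 = 0.515, a bias of +1.5 points.
- 48/32, q = 0.75: (12 + 24)/80 = 0.450, a bias of −5 points.

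Blocking alone allows little imbalance. A list of 48 ends eight places into a block of ten, so at worst 5:3. Two lists leaning the same way give 50/46. At q = 0.70 that is (50 × 0.30 + 46 × 0.70)/96 = 0.492.

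**Step 2. Why the balanced test is conservative.** The true null variance of the count preferring test is 80·q(1 − q): 20.0 at q = 0.50, 18.2 at 0.65 and 15.0 at 0.75. The binomial test always uses 80 × 0.25 = 20.

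**Step 3. Type I error of the exact two-sided binomial test.** The count is the sum of Bin(nA, 1 − q) and Bin(nB, q). With 80 respondents the test rejects at 30 or fewer, or 50 or more.

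| Split A/B | q = 0.50 | q = 0.65 | q = 0.75 |
|---|---|---|---|
| 40/40 | 3.3% | 2.5% | 1.4% |
| 44/36 | 3.3% | 3.1% | 2.7% |
| 48/32 | 3.3% | 5.0% | 7.7% |

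A 48/32 split means that all 16 planned losses (96 − 80) fall in one arm.

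**Step 4. Power, binomial against Fisher's test of preferred period by arm.** The probabilities of preferring test are pA = expit(0.65 − logit q) and pB = expit(0.65 + logit q). At q = 0.65 these are 0.508 and 0.781, averaging 0.644. At q = 0.75 they are 0.390 and 0.852, averaging 0.621.

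| Split A/B | q | Binomial | Fisher by order |
|---|---|---|---|
| 40/40 | 0.50 | 76.6% | 76.6% |
| 40/40 | 0.65 | 69.2% | 70.3% |
| 40/40 | 0.75 | 51.8% | 61.4% |
| 44/36 | 0.50 | 76.6% | 79.1% |
| 44/36 | 0.65 | 59.3% | 74.2% |
| 36/44 | 0.65 | 78.0% | 72.5% |

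The unbalanced rows need care. At 44/36 about 2.5 points of the gap (79.1 − 76.6) appear with no order effect at all and come from the discreteness of the tests. The rest is mainly the downward bias of the pooled share. At 36/44 the same bias works in favour of test, so the higher pooled figure is not a real gain. The 40/40 rows are the cleaner comparison.

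**The case against.** A reader might infer that the plan attributes any preference for the later or earlier product to the products themselves. The document does not support that. Order is randomised in centralised blocks, 1:1 allocation is implied, and with equal numbers answering per arm the expected share under no product effect is exactly one half whatever the order effect. The test then errs on the safe side.

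Imbalance among respondents is not a planned feature. Section 4.1 also lets subjects who cannot finish a period move on to the next instead of leaving, which limits one-sided loss. Neither a 44/36 split nor 65% recency comes from the document, and at those values type I error is still 3.1%.

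The consequence is small. Preference is exploratory, the pass/fail rule in section 11.4 concerns skin endpoints only, and section 11.1 states: "As it is an exploratory study no adjustment for multiple testing will be applied". The contrast with the other models is also softer than it looks, since section 11.1 allows non-significant fixed effects to be dropped.

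On product type, a single pooled test is inferred from silence, and section 11.1 already has endpoints summarised by product type. That is a separate and minor matter: ignoring type does not turn an order effect into a product effect.

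All of this stands as a limit on weight. It does not remove the point that the test leaves out the order that the trial randomised, or that the 20% drop-out allowed for in section 11.2 need not fall equally on the two arms.

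**Conclusion.** The point holds as a minor analysis improvement. With balanced respondents the planned test is valid, but conservative and less powerful. At 40/40 it loses about 1 point of power at 65% recency and about 10 points at 75% (51.8% against 61.4%), and nothing without an order effect. With unequal respondents the pooled share is also biased, by 1.5 points in either direction at 44/36 and 65% recency. Of the settings in the type I error table, only 48/32 with 75% recency exceeds 5% (7.7%).

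These sizes rest on assumed recency, an assumed product effect, 80 respondents and a two-sided exact test. They do not support a claim that the preference result would generally be wrong, and the 59% against 74% contrast at 44/36 should not be read as the typical cost.

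**What to change.** In section 11.1, replace the binomial test for preference by one of these:

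- A Mainland-Gart/Fisher test of preferred period (first or second) by arm. With no product effect, both arms have the same chance of choosing the second-period product, so the order effect drops out.
- A logistic model for preferring test, with sequence and product type. Code sequence as ±½ and centre product type, so that the intercept carries the order-adjusted product preference.

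Report the preference as (pA + pB)/2, the average of the two arm-specific proportions, with a confidence interval. As a separate minor addition, give it by 1-piece and 2-piece type as well as overall, and state that the test is two-sided.

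The cost is a sentence or two in section 11.1. The answers, the arm and the product type are already collected, so no extra data or subject burden is involved.

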11.2. Sample size

The itching score is given at each baseplate change and the max of these scores per week at steady state is the primary endpoint. The max score is only calculated if there are measurement for more than four days within a week. For each subject approximately three measurements will be available for each test period.

The sample size calculation is based on a simplified linear mixed model with only 1-pc users and no period effect (corresponding to the design from CP300). The model includes a fixed effect of product (comparator and test product), a random effect of subject and a random interaction effect of product and subject.

Based on data from CP300 it is assumed that the total standard deviation of the primary endpoint is 1.82 and that the total variation 1.82² is divided so that:

- a random effect of subject accounts for 68% of the total variation
- a random interaction effect of product and subject accounts for 0%
- and the residual accounts for 32% of the total variation

In table 1 the needed sample size is calculated by simulation for varying values of the true difference between comparator and test product regarding mean max itching score per week and for different values of the power to demonstrate that the difference is significantly different from 0.

Table 4: Subjects needed for comparing mean max itching score between two products

True difference	Reduction in mean if the mean for the comparator is 2.2 as for [REDACTED] in CP300	Power		
		0.8	0.85	0.9
0.6	27%	46	>46	>46
0.7	32%	35	40	45
0.8	36%	30	32	36

Based on the numbers in the table, 40 subjects should test each product to ensure a power of 85%, if the true difference between the comparator product and a test product is 0.7 (corresponding to a 32% reduction if the mean for the comparator is 2.2 as in CP300). This will be enough when comparing the two products. 1-pc and 2-pc users will be evaluated separately (in a combined model). As there are no previous data for 2-pc users the sample size calculations for 1-pc users is assumed to cover 2-pc users as well. To take a potential drop-out (20%) into account it is recommended to include a total of 48 1-pc and 48 2-pc users, resulting in a total of 96 subjects.

If a carry-over effect is present and therefore data from only the first period is analysed as a parallel arm trial 40 subjects (20 in each arm) will ensure a power of 82% if the true difference between the comparator product and the test product is 1.7. If there are no significant difference between 1- and 2-pc users, 80 subjects (40 in each arm) will ensure a power of 83% if the true difference between the comparator product and the test product is 1.2 (the difference in CP300 was estimated to 1.3).

The total number of 80 subjects is the required number of subjects for the [REDACTED]

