In light of the data obtained it might be considered to make additional explorative analyses based on a subset of the ITT/PP population.

Analysis of the primary endpoint

Max itching score within a week at steady state will be analysed by a mixed repeated measures model using individual week max scores (on a scale from 0-10) as the observational unit. The model will consider that observations corresponding to different subjects are independent; whereas observations corresponding to the same subject are correlated. The correlation between observations corresponding to the same product can be larger than observations corresponding to different products. Hence the model includes a fixed effect of product (comparator product, test product), a fixed effect of product type (1- or 2-pc), a fixed interaction between product and product type, a fixed period effect, an interaction between period and product, a random effect of subject and a random interaction effect of product and subject.

The model might be reduced by removing non-significant fixed effects, if relevant. The interaction between period and product allows for a possible carry-over effect. It is assumed that a possible carry-over effect is the

CONFIDENTIAL

same for 1- and 2-pc users. If the interaction is significant, data from only the first test period will be analysed as a parallel arm study because the first period is free of carry-over effects and period will be excluded from the model.

All combinations of differences between the two products will be estimated for both 1- and 2- pc products. Furthermore, differences for same product between product types will be estimated (if the model is not reduced).

Analysis of the secondary endpoints

The endpoints regarding pain, burning, physical discomfort, ability to move around and the overall ability to stick the baseplate to the skin (on a scale from 0-10) will be analysed by the same model as the primary endpoint starting by calculating the max within a week at steady state.

[REDACTED] endpoints regarding bleeding (Y/N), experiencing any weeping or moisture (Y/N) and Ulcers or sores (Y/N) per baseplate change at steady state will be analysed by a repeated logistic regression model with the same effects included as for the primary endpoint.

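### The powers in section 11.2 fit one weekly score per period, but the plan expects and analyses about three; on its stated inputs, 40 completers have 99.9% power at a difference of 0.7, not 85%

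*Combined protocol and SAP*

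**What the plan says.** Section 11.2 sizes the trial on a simplified mixed model for 1-piece users, with a fixed product effect, a random subject effect and a random product-by-subject effect. From the earlier study CP300 it takes a total SD of 1.82. Of that variance it gives 68% to subject and 32% to residual, and says that "a random interaction effect of product and subject accounts for 0" per cent. Table 4 follows by simulation, and the conclusion drawn from it is that "40 subjects should test each product to ensure a power of 85" per cent at a difference of 0.7.

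On the amount of data, section 11.2 says "For each subject approximately three measurements will be available for each test period". Section 11.1 fits the primary model "using individual week max scores (on a scale from 0-10) as the observational unit". Appendix 1 defines steady state as the last three weeks of each period.

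If carry-over forces a first-period analysis, section 11.2 states that "40 subjects (20 in each arm) will ensure a power of 82% if the true difference" is 1.7, and that "80 subjects (40 in each arm) will ensure a power of 83% if the true difference" is 1.2 when the two product types are pooled. Section 11.3 gives no power of its own and refers back to section 11.2.

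**The concern.** Averaging over repeated weeks reduces residual variance. With the interaction set to 0%, residual variance is the only noise in the within-subject comparison, so the number of weekly scores has a large effect on power. Section 11.2 announces about three scores per period and then prints powers that look like those for one.

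The model simulated also points to repeated scores. For the DET score, section 11.1 explains that "the random interaction effect of product and subject is not included, as there is only one measurement per subject for each product". By that reasoning, a sample-size model that keeps the interaction presupposes more than one score per product.

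At stake is what the trial can detect. A reader cannot tell whether 40 completers have 85% power for a difference of about 0.7 or about 0.4, and that affects how a small or null result is read. If it is the variance split that is misstated, the apparent surplus power does not exist.

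**Working it through.** **Inputs.** From section 11.2: SD 1.82 (variance 1.82² = 3.3124), split 68/0/32, 40 completers, difference 0.7. From section 11.3: 5% significance level. I take the test as two-sided because section 11.2 describes showing a difference from 0. Let k be the number of weekly scores per subject per period.

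**Cross-over.** With no interaction variance, a subject's difference between product means has variance 2 × 0.32 × 3.3124 / k = 2.120 / k. Power is from the noncentral t distribution with n − 1 degrees of freedom and noncentrality 0.7 / (SD/√40).

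| k | SD of difference | SE, n = 40 | 0.7 / SE | Power | Difference detectable at 85% |
|---|---|---|---|---|---|
| 1 | 1.456 | 0.230 | 3.04 | 84.3% | 0.71 |
| 2 | 1.030 | 0.163 | 4.30 | 98.7% | 0.50 |
| 3 | 0.841 | 0.133 | 5.27 | 99.9% | 0.41 |

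The stated 85% is reproduced at k = 1 only. A simulation of 100,000 trials gave 0.843 for k = 1, 0.987 for k = 2 and 0.999 for k = 3. Two other readings do not explain the figure: a one-sided 5% test at k = 1 gives 91.9%, and independent groups of 40 give 41% at k = 1 or 49% at k = 3.

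**Table 4.** Subjects needed for 80/85/90% power:

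| True difference | Plan | k = 1 | k = 2 | k = 3 |
|---|---|---|---|---|
| 0.6 | 46 / >46 / >46 | 49 / 55 / 64 | 26 / 29 / 33 | 18 / 20 / 23 |
| 0.7 | 35 / 40 / 45 | 36 / 41 / 48 | 19 / 22 / 25 | 14 / 15 / 18 |
| 0.8 | 30 / 32 / 36 | 28 / 32 / 37 | 16 / 17 / 20 | 11 / 12 / 14 |

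All seven numeric cells lie within 3 subjects of the k = 1 column. Solving each printed size and power for k gives values from 0.93 to 1.06. With k = 3, every printed size has at least 99.7% power.

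**First-period analysis.** This is a two-sample t test with SD 1.82 × √(0.68 + 0.32/k), that is 1.82, 1.67 and 1.61 for k = 1, 2 and 3.

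| Setting | Plan | k = 1 | k = 2 | k = 3 |
|---|---|---|---|---|
| 20 per arm, difference 1.7 | 82% | 82.1% | 88.1% | 90.1% |
| 40 per arm, difference 1.2 | 83% | 83.0% | 88.8% | 90.7% |

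The printed powers imply SDs of 1.822 and 1.819, which is the full 1.82 with no averaging over weeks.

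**Sensitivity to the 0%.** Move a share s of the 32% into the interaction and keep k = 3 and n = 40. The variance of the difference becomes 2 × 3.3124 × (s + (0.32 − s)/3). Power at 0.7 is 99.4% for s = 5%, 98.1% for 10%, 92.8% for 20%, 85% for about 31% and 84.3% for the full 32%.

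**The case against.** The best defence is that this is an unstated input and not an arithmetic error. Every printed power can be reached from the stated SD and split with one score per period. Section 11.2 says three scores will be available, not that three were simulated, and it ties the calculation to a CP300 design that the reader cannot see. A deliberately cautious basis would print the same numbers. That is possible, but the plan does not say so, and one score is not what it expects or analyses.

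Second, 99.9% depends on an interaction of exactly 0% and on independent weekly residuals. Neither is certain: section 11.1 itself allows scores on the same product to be more alike. With first-order autoregressive residuals at correlations of 0.3, 0.5 and 0.7 (assumed values), power with three scores is 98.9%, 96.7% and 92.7%. This stands as a caution on the size of the discrepancy. It does not restore 85%: that needs about 31 of the 32 residual points to be interaction, against the plan's stated 0%.

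Third, if CP300 had only one score per product, interaction and residual could not be separated there and the 0% would carry no information. The documents cannot settle this, so the split may be the faulty item.

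Fourth, three usable weeks are less secure for 2-piece users. A weekly maximum needs measurements on more than four days, and section 5.1.6 expects two baseplates every three days, or 7 × 2/3 ≈ 4.7 a week. That is fair, but Table 4 is for 1-piece users, whom section 5.1.6 expects to change daily. Even two usable weeks give 98.7%.

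**Conclusion.** The printed inputs, the expected number of weekly scores and the printed powers cannot all describe the planned analysis. The SD and split fit the figures with one score per period; no printed figure fits two or three. The likely cause is that the repeat weeks were left out of the calculation, although the plan does not give enough to prove it.

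Taking the plan's 0% interaction and independent weekly residuals at face value, 40 completers have 99.9% power at 0.7, and the first-period powers are 90.1% and 90.7%. On those terms the error is conservative for both analyses. It gives no reason to change the number of subjects, and section 11.2 adds that "The total number of 80 subjects is the required number of subjects for the" purpose whose description is redacted. It should still be corrected, because section 11.2 is the plan's only statement of power.

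**What to change.** State in section 11.2 how many weekly scores per period were simulated and where the 0% interaction came from. Then take one of these routes:

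1. **Restate.** Rerun Table 4 and the 85%, 82% and 83% figures with the expected number of usable weeks. For example: *With 40 1-piece completers, total SD 1.82 and the CP300 split, power at a difference of 0.7 is 84.3%, 98.7% or 99.9% with one, two or three weekly scores per period; the difference detectable with 85% power is 0.71, 0.50 or 0.41.* A line on the interaction share (98.1% at 10% and 92.8% at 20%, with three scores) would be a useful addition.
2. **Declare.** Keep the figures and add: *The calculation uses one weekly score per period as a deliberately conservative basis; the analysis uses all available weekly scores.*
3. **Correct the split**, if the check shows that the variance shares are what is misstated, and confirm that the powers follow from the corrected shares.

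The cost is one sentence, or one rerun of the simulation with restated figures. If the stated inputs are right, neither the design nor the number of subjects changes.
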